A Single-center, Randomized, Open-label Phase Ib/IIa Clinical Study to Evaluate the Safety, Tolerability, Pharmacokinetics, and Preliminary Efficacy of Helicobacter Pylori Eradication after Multiple Doses of TNP-2198 Capsules Combined with Rabeprazole Sodium Enteric-Coated Tablets, and Multiple Doses of TNP-2198 Capsules Combined with Rabeprazole Sodium Enteric-Coated Tablets and Amoxicillin Capsules in Asymptomatic Healthy Participants with Positive Helicobacter Pylori Infection

Protocol Synopsis

Protocol No.: TNP-2198-04

Approval Date: 20 June 2021

Protocol Synopsis

Study Title	A Single-center, Randomized, Open-label Phase Ib/IIa Clinical Study to Evaluate the Safety, Tolerability, Pharmacokinetics, and Preliminary Efficacy of Helicobacter Pylori Eradication after Multiple Doses of TNP-2198 Capsules Combined with Rabeprazole Sodium Enteric-Coated Tablets, and Multiple Doses of TNP-2198 Capsules Combined with Rabeprazole Sodium Enteric-Coated Tablets and Amoxicillin Capsules in Asymptomatic Healthy Participants with Positive Helicobacter Pylori Infection
Study Objectives	
Primary Objectives:
 
 1 To evaluate the safety and tolerability of multiple doses of TNP-2198 Capsules combined with Rabeprazole Sodium Enteric-coated Tablets, and multiple doses of TNP-2198 Capsules combined with Rabeprazole Sodium Enteric-coated Tablets and Amoxicillin Capsules in asymptomatic healthy participants with positive Helicobacter pylori infection; 2 To evaluate the pharmacokinetics of multiple doses of TNP-2198 (including major metabolites), rabeprazole, and amoxicillin in each treatment group. 
Secondary Objectives:
 
To evaluate the preliminary efficacy of multiple-dose combination of TNP-2198 Capsules and Rabeprazole Sodium Enteric-coated Tablets and multiple-dose combination of TNP-2198 Capsules, Rabeprazole Sodium Enteric-coated Tablets and Amoxicillin Capsules in the eradication of Helicobacter pylori.

Clinical Study Protocol No.	TNP-2198-04
Sponsor	TenNor Therapeutics
Clinical Trial Notification No.	CXHL1800160/161
Study Facility	Phase I Drug Clinical Study Center of the First Bethune Hospital of Jilin University
Study Phase	Phase Ib/IIa
Investigational Products	
TNP-2198 Capsules Manufacturer: WuXi STA (Shanghai) Co., Ltd. (entrusted) Strength: 100 mg Storage Condition: Preserve in tightly closed containers, protected from light and stored at ambient temperature (10-30 °C)
 
Rabeprazole Sodium Enteric-coated Tablets Manufacturer: Eisai China Inc. Drug Approval No.: GuoYaoZhunZi H20090090 Strength: 20 mg Storage Condition: Preserve in tightly closed containers, protected from light and stored below 25 °C
 
Amoxicillin Capsules Manufacturer: Zhuhai United Laboratories (Zhongshan) Co., Ltd. Drug Approval No.: GuoYaoZhunZi H44021351 Strength: 0.25 g Storage Condition: Below 25 °C

Study Design	Participants: 40 asymptomatic healthy participants positive for Helicobacter pylori infection, males and females.

	
The study is designed to evaluate the safety, tolerability, and pharmacokinetics of multiple doses of TNP2198 Capsules combined with Rabeprazole Sodium Enteric-coated Tablets, and multiple doses of TNP-2198 Capsules combined with Rabeprazole Sodium Enteric-coated Tablets and Amoxicillin Capsules in asymptomatic healthy participants with positive Helicobacter pylori infection, and to evaluate the preliminary efficacy of each dosage regimen for Helicobacter pylori eradication.
 
A total of 4 treatment groups will be set up in this study and the participants will be randomized at a ratio of 1: 1: 1: 1.
 
 • Group A: TNP-2198 Capsules 200 mg twice daily (BID) + Rabeprazole Sodium Enteric-coated Tablets 20 mg BID (n=10); • Group B: TNP-2198 Capsules 400 mg BID + Rabeprazole Sodium Enteric-coated Tablets 20 mg BID (n=10); • Group C: TNP-2198 Capsules 600 mg BID + Rabeprazole Sodium Enteric-coated Tablets 20 mg BID (n=10); • Group D: TNP-2198 Capsules 400 mg BID + Rabeprazole Sodium Enteric-coated Tablets 20 mg BID + Amoxicillin Capsules 1 g BID (n=10). 
Screening will occur within 14 days of the first dose of study investigational products. All participants will provide informed consent and undergo Screening evaluations to determine their eligibility. Eligible participants will be admitted to the clinical study center on day -1 (the day before dosing, D-1). On Day 1 to Day 14, breakfast and dinner will be completed within 30 minutes prior to dosing, and the investigational products will be administered after meals. On Day 15, breakfast will be completed within 30 minutes prior to dosing, and the last dose will be administered after meals. Pharmacokinetic blood samples will be collected at the time points scheduled in the protocol during the study, and the safety tolerability evaluation and ¹⁴C urea breath test (UBT) will be conducted.
 
All participants will be discharged after completion of the safety and tolerability evaluation on Day 17 and return to the clinical study center for a follow-up UBT test between Days 44 and 50 to evaluate the preliminary efficacy of Helicobacter pylori eradication.

Screening Evaluations	
Participants will be screened from D-14 to D-2.
 
Screening evaluations: demographic information (including sex, ethnicity, age, weight, height and BMI), medical history, surgical history, smoking history, reproductive status, drinking history/diet, prior medications, physical examination, vital signs (blood pressure, pulse rate, respiratory rate and body temperature), 12-lead ECG, chest plain X-ray, abdominal Doppler ultrasound (digestive system + urinary system), clinical laboratory tests (hematology, blood biochemistry, urinalysis and coagulation function), infectious disease tests (hepatitis B serologic test, hepatitis C antibody, hepatitis C core antigen, HIV antigen/antibody, treponema pallidum antibody [an additional rapid plasma regain (RPR) test is required in patients positive for treponema pallidum antibody]), serum pregnancy test (females only) and UBT.
 
Note: The test results of hepatitis B virus, hepatitis C antibody, hepatitis C core antigen, HIV antigen/antibody and treponema pallidum antibody are valid within 3 months; Chest anteroposterior radiograph valid within 1 year; Abdominal Doppler ultrasound valid within 1 month.

Admission (Baseline) Evaluations	
Admission (baseline) will be occurred on D-1.
 
Baseline evaluations: Medical history, surgical history, clinical laboratory tests, physical examination, vital signs, 12-lead ECG, serum pregnancy test (females only), urine drug screen (morphine, marijuana), alcohol breath test, UBT.
 
Note: Screening results are valid within 7 days for clinical laboratory tests and UBT.

Dosing Regimen	
The investigational products shall be orally administered twice daily after completion of meals, for 14 consecutive days. On Day 15, the participants have breakfast within 30 minutes prior to dosing, and the last dose shall be taken after completion of meals. Each participant takes 29 doses of the investigational product. The dose of the investigational product for each group are as follows:
 
 • Group A: TNP-2198 Capsules 200 mg/time, i.e. 2 capsules/time; Rabeprazole Sodium Enteric-coated Tablets, 20 mg/time, i.e., 1 tablet/time;

	
 Group B: TNP-2198 Capsules 400 mg/time, i.e., 4 capsules/time; Rabeprazole Sodium Enteric-coated Tablets, 20 mg/time, i.e., 1 tablet/time; Group C: TNP-2198 Capsule 600 mg/time, i.e. 6 capsules/time; Rabeprazole Sodium Enteric-coated Tablets, 20 mg/time, i.e., 1 tablet/time; Group D: TNP-2198 Capsules 400 mg/time, i.e., 4 capsules/time; Rabeprazole Sodium Enteric-coated Tablets, 20 mg/time, i.e., 1 tablet/time; Amoxicillin Capsules, 1 g/time, i.e., 4 capsules/time.
Inclusion Criteria	
Participants must meet all of the following criteria to be enrolled:
 
 1 Have signed the informed consent form before the study, and fully understand the study contents, process and possible adverse reactions; 2 Participants who are able to complete the study as required by the protocol; 3 Participants are willing to have no pregnancy plan within 6 months after last dose of investigational products and voluntarily take effective contraceptive measures; 4 Male and female participants aged 18-65 years (inclusive); 5 Male participants weighing not less than 50 kg and female participants weighing not less than 45 kg; Body mass index within the range of 18-30 kg/m² (inclusive); 6 Health status: participants do not have history of clinically significant cardiovascular, liver, kidney, digestive tract, nervous system, respiratory system, mental disorder and metabolic disorder; 7 Physical examination and vital signs are normal or abnormal but not clinically significant as judged by the investigator; 8 Participants whose ¹⁴C urea breath test (UBT) results are positive. 9 Clinical laboratory test results are within normal range or abnormal but not clinically significant as judged by the investigator.
Exclusion Criteria	
Participants were not to be enrolled if they met any of the following exclusion criteria:
 
 1 History of helicobacter pylori eradication therapy (including participation in other clinical studies for helicobacter pylori eradication); 2 Those who smoked more than 5 cigarettes per day in the 3 months prior to screening; 3 Those who are allergic to the investigational product or its excipients, or participants with allergic constitution (multiple drug and food allergies); 4 Those who have a history of drug and/or alcohol abuse (average weekly consumption of \geq 14 units of alcohol: 1 unit = 285 mL of beer, or 25 mL of spirits, or 100 mL of wine); 5 Those who have blood donation or massive blood loss ($>$ 450 mL) within 3 months prior to screening; 6 Those who have taken any drug that changes the activity of liver enzyme within 28 days prior to screening; 7 Those who have taken any prescription drugs, over-the-counter drugs, any vitamin products, or herbal remedies within 14 days prior to screening; 8 Those who have taken special diet (including pitaya, mango, grapefruit, etc.) or have had strenuous exercise within 2 weeks prior to screening, or other factors affecting drug absorption, distribution, metabolism, excretion, etc.; 9 Those who have had a major change in diet or exercise habits recently; 10 Those who have taken the other study drug or participated in the other clinical study that have not been finished within 1 month prior to administration of the investigational product; 11 Those who have a history of dysphagia or any gastrointestinal disease affecting drug absorption; 12 Those who have any disease that increases the risk of bleeding, such as hemorrhoids, acute gastritis or gastric and duodenal ulcers; 13 Those who have abnormal ECG with clinical significance; 14 Female participants who are in lactation or have a positive result in serum pregnancy test at screening or during the course of the study;

	
15 Those with symptoms of cardiovascular, digestive, respiratory, urinary, neurological, hematological, immunological, endocrine system or tumor, and mental illness or with past medical history that has not been cured;
 
16 The following diseases (including but not limited to gastrointestinal, renal, hepatic, neurologic, hematologic, endocrine, oncologic, pulmonary, immunologic, psychiatric or cardiovascular and cerebrovascular diseases) with clinically significant abnormalities in clinical laboratory tests or other clinical findings;
 
17 Viral hepatitis (including hepatitis B and C), HIV antibody, treponema pallidum antibody positive (those with positive treponema pallidum antibody need additional RPR test);
 
18 Acute illness or concomitant medication from the time of signing the informed consent form to the time before administration of the investigational product;
 
19 Consumption of chocolate, any caffeine-containing or xanthine-rich food or beverages within 48 hours prior to administration of the investigational product;
 
20 Those who have taken any alcohol-containing products within 48 hours prior to administration of investigational product;
 
21 Those with a positive result in urine drug screening or a history of drug abuse or drug use within the past 5 years;
 
22 Other conditions considered unsuitable for participation in the study by the investigator.

Safety and Tolerability Evaluation	
CTCAE 5.0 criteria are used.
 
All participants are observed for any adverse events occurring during the clinical study, and their clinical manifestations, severity, onset time, end time, treatment measures and outcome are recorded, and their correlation with the investigational product shall be determined.
 
Safety and tolerability evaluation includes adverse events (AE), clinical laboratory tests (hematology, blood biochemistry, coagulation, urinalysis), vital signs (blood pressure, pulse rate, respiratory rate and body temperature), 12-lead electrocardiogram (ECG) and physical examination.

Pharmacokinetics Sample Collection and Processing Methods	
The test sample is plasma and the test substances are: TNP-2198 (including major metabolites), rabeprazole and amoxicillin.
 
Collection time points:
 
 Day 1: within 30 minutes before breakfast, 0.5, 1, 1.5, 2, 2.5, 3, 3.5, 4, 5, 6, 7, 8, 9, 10, 11, and 12 h after dosing (prior to the second dose of the day); Days 3, 5, 7, 9, 11, 13, and 14: within 30 min before breakfast; Day 15: within 30 minutes before breakfast and 0.5, 1, 1.5, 2, 2.5, 3, 3.5, 4, 5, 6, 7, 8, 9, 10, 11, 12, 24 (Day 16) and 48 (Day 17) h after dosing. 
Processing method:
 
Whole blood is collected in vacuum blood collection tubes containing anticoagulant, 4 mL per tube, and plasma is obtained by centrifugation after completion of whole blood collection, and the plasma samples are divided into two aliquots and stored in a refrigerator at -80 °C, one for pharmacokinetics analysis and the other as a backup. The process from sample collection to the refrigerator at -80 °C storage needs to be completed within 1 hour. Refer to the Laboratory Operation Manual for specific operation requirements.

PK Parameters	
First dose PK parameters include at least:
 
 Time to peak concentration (T_{max}) Peak concentration (C_{max}) Elimination half-life ($t_{1/2}$) Area under the plasma concentration-time curve from the first dose extrapolated to infinity ($AUC_{0-\infty}$) Area under the plasma concentration-time curve from the first dose to the dosing interval (12 h) ($AUC_{0-\tau}$)

	
 • Apparent volume of distribution (V_d/F) • Apparent clearance (CL/F) 
Last dose PK parameters include at least:
 
 • Time to peak ($T_{max,ss}$) • Maximum plasma concentration at steady state ($C_{max,ss}$) • Minimum plasma concentration at steady state ($C_{min,ss}$) • Mean plasma concentration at steady state ($C_{avg,ss}$) • Elimination half-life ($t_{1/2,ss}$) • Area under the plasma concentration-time curve from the last dose to the last measurable concentration time point ($AUC_{0-last, ss}$) • Area under the plasma concentration-time curve from the last dose to the dosing interval (12 h) ($AUC_{0-tau,ss}$) • Area under the plasma concentration-time curve from the last dose extrapolated to infinity ($AUC_{0-infty, ss}$) • Apparent volume of distribution at steady state (V/F_{ss}) • Apparent clearance (CL/F_{ss}) • Accumulation Index (R_{ac}): $AUC_{0-tau,ss}$ on Day 15/AUC_{0-tau} on Day 1 • Fluctuation index (DF): Percentage fluctuation at steady state = $100 \times (C_{max,ss} - C_{min,ss})/C_{avg, ss}$
Preliminary Evaluation of Helicobacter pylori Eradication	
All participants will undergo a total of 4 UBT tests (under fasting conditions before breakfast) at baseline, Day 8, Day 16, and Day 44-50 after last dosing, to evaluate the preliminary efficacy in the eradication of Helicobacter pylori.

Statistical Analysis	
Safety and tolerability analysis
 
The analysis of safety and tolerability are mainly based on descriptive statistics. AEs, serious adverse events (SAEs), drug-related AEs and AEs leading to withdrawal from the study are summarized.
 
The number of participants, number of AEs and incidence of all AEs will be tabulated and summarized by treatment group, system organ class and preferred term.
 
The incidence of adverse events (occurring separately in each treatment group, both in 2 groups, or in 3 groups) in each treatment group will be tabulated and described according to CTCAE grade by treatment group.
 
The number of participants, number of AEs and incidence of AEs in each treatment group will be tabulated according to severity and relationship to the investigational product by system organ class and preferred term.
 
The laboratory test results that are normal before the test but abnormal after treatment are described by treatment group.
 
The mean, standard deviation, median, minimum and maximum values of vital signs (blood pressure, respiratory rate, pulse rate and body temperature) and laboratory test before and after administration are calculated according to the treatment group, respectively. If necessary, paired t test or non-parametric test can be used for comparison before and after administration.
 
SAE and suspected unexpected serious adverse reactions (SUSARs) are presented separately.
 
Pharmacokinetic parameter analysis

Plasma concentrations will be summarized descriptively by treatment group and time point, including: arithmetic mean, standard deviation, minimum, median, maximum, geometric mean, coefficient of variation, geometric coefficient of variation. Descriptive analysis will be performed for the pharmacokinetic parameters calculated after the first and last administration by treatment group, including: arithmetic mean, standard deviation, minimum, median, maximum, geometric mean, coefficient of variation, geometric coefficient of variation, etc. In addition, the accumulation index $AUC_{0-\tau,ss}$ (D15)/ $AUC_{0-\tau}$ (D1) is calculated. Mean and individual concentration-time curves are displayed by linear and semi-logarithmic plotting. Analysis of variance or non-parametric test will be performed on pharmacokinetic parameters between each treatment group.

Preliminary analysis of *Helicobacter pylori* eradication

The preliminary eradication effect analysis will be based on the full analysis set, which is defined as all participants who are randomized and receive at least one dose of investigational product. The preliminary efficacy of *Helicobacter pylori* eradication will be analyzed descriptively by frequency (percentage) of 4 UBT test results (negative or positive) at baseline, on Day 8, Day 16 and Day 44-50 after last dosing in different treatment groups, and inter-group comparison will be performed. Fisher's exact test will be used for inter-group comparison. As an auxiliary analysis, the mean, standard deviation, median, minimum, maximum, and change from baseline will be presented for UBT values. Inter-group comparisons of UBT values will be analyzed using the model of analysis of covariance or mixed-effects model repeated-measures (MMRM) with baseline UBT values as a covariate, treatment group and dose group as a fixed variable. If the model of analysis of covariance was used, the last observation carried forward (LOCF) was used to impute missing values.

There are no clear statistical hypotheses in this study and all statistical tests are exploratory test with a two-sided 5% nominal significance level. The statistical analysis method and plan are detailed in the statistical analysis plan.

Schedule of Activities

Study Procedures		Screening Visit (D-14-D-2)	D-1	D1	D2-14	D15	D16	D17	Follow-up (during D44-50)
Screening	Signing of ICF	X							
	Demographics	X							
	Medical and surgical history	X	X						
	Concomitant medications	X	X	X	X	X	X	X	X
	Chest plain X-ray	X							
	Abdominal Doppler ultrasound (digestive system + urinary system)	X							
	Infectious disease screening (hepatitis B serologic test, hepatitis C core antigen, hepatitis C antibody, HIV antigen/antibody, treponema pallidum antibody)	X							
	Breath alcohol test		X						
	Urine drug screening (morphine, marijuana)		X						
	Blood pregnancy test	X	X					X	
Enrollment	Verification of inclusion and exclusion criteria	X	X						
	Admission		X						
Study treatment administration	Randomization		X						
	Dosing			X	X	X			
	Clinical laboratory tests (blood routine, blood biochemistry, coagulation, urine routine)¹	X	X		X			X	

Safety and tolerability Assessment	Physical examination²	X	X		X			X	
	12-lead ECG³	X	X	X		X		X	
	Vital signs⁴	X	X	X	X	X	X	X	
	Monitoring and recording of adverse events			X	X	X	X	X	X
PK sample collection	Blood sample⁵			X	X	X	X	X	
Preliminary efficacy of Hp eradication	¹⁴ C-urea breath test ⁶	X	X		X		X		X
End of study	Discharge							X	
	Follow-up, study completion								X

Note:

- 1 Clinical laboratory tests will be performed at the screening period, baseline period, D4, D6, D8, D12 (before the first dose), and D17 (48 h after dosing on D15). The results of screening examination within 7 days can be used for the baseline period, and no additional test will be required.
- 2 Physical examination will be performed at the screening period, baseline period (D-1), D4, D6, D8, D12 and D17.
- 3 12-lead ECG will be performed at the screening period, baseline period (D-1), D1 (2 h after the first dose), D15 (within 60 min before and 2 h after dosing) and D17 (48 h after dosing on D15).
- 4 Vital signs will be examined at the screening period, baseline period (D-1), D1 (within 60 min before the first dose and 0.5 h, 2 h, 4 h, 8 h, 12 h after dosing), D2-14 (within 60 min before the first dose), D15 (within 60 min before dosing and 0.5 h, 2 h, 4 h, 8 h, 12 h after dosing), D16 (24 h after dosing on D15) and D17 (48 h after dosing on D15).
- 5 PK blood samples will be collected on D1 (within 30 min before breakfast, and 0.5 h, 1 h, 1.5 h, 2 h, 2.5 h, 3 h, 3.5 h, 4 h, 5 h, 6 h, 7 h, 8 h, 9 h, 10 h, 11 h, 12 h after dosing), within 30 min before breakfast on D3, D5, D7, D9, D11, D13 and D14, on D15 (within 30 min before breakfast, and 0.5 h, 1 h, 1.5 h, 2 h, 2.5 h, 3 h, 3.5 h, 4 h, 5 h, 6 h, 7 h, 8 h, 9 h, 10 h, 11 h, 12 h after dosing), D16 (24 h after dosing on D15) and D17 (48 h after dosing on D15).
- 6 UBT will be performed in fasting state before breakfast and will be performed on D8 during D2-14; the results of screening examination within 7 days can be used for the baseline period, and no additional test will be required

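### The synopsis's only categorical laboratory display counts normal-to-abnormal results, so worsening from an eligible abnormal baseline cannot appear in it; add a shift table and a thresholded listing

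*Combined protocol and SAP*

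**What the plan says.** Four parts of the Protocol Synopsis bear on this.

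- **Statistical Analysis, Safety and tolerability analysis.** The categorical rule for laboratory data is: "The laboratory test results that are normal before the test but abnormal after treatment are described by treatment group". The same section says that descriptive statistics (mean, SD, median, minimum, maximum) for vital signs and "laboratory test before and after administration are calculated according to the treatment group, respectively". It then adds: "If necessary, paired t test or non-parametric test can be used for comparison before and after administration". AEs are tabulated by CTCAE grade, severity and relationship to the product.
- **Inclusion Criteria, item 9.** The eligibility condition is: "Clinical laboratory test results are within normal range or abnormal but not clinically significant as judged by the investigator". Exclusion criterion 16 works in the same direction, removing listed diseases "with clinically significant abnormalities in clinical laboratory tests or other clinical findings".
- **Safety and Tolerability Evaluation.** The section opens with "CTCAE 5.0 criteria are used" and names four laboratory panels: hematology, blood biochemistry, coagulation and urinalysis.
- **Schedule of Activities, note 1.** Laboratory tests are done at screening, at baseline and on D4, D6, D8, D12 and D17. A screening result within 7 days may stand in for baseline.

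The closing paragraph of the Statistical Analysis section refers to a separate SAP for detail. The text of that SAP is not in the document reviewed.

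**The concern.** The eligibility rule and the laboratory display do not match. Eligibility lets a participant enter with a value outside the normal range. The display counts only people who enter inside it. For an analyte that is abnormal at baseline, no post-dose value, however extreme, can meet the display's condition.

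Safety and tolerability is the first primary objective, and its analysis is mainly descriptive, so the choice of displays largely decides what a reader sees. With 10 participants per group, much of the laboratory safety reading comes from individual changes. The stated display leaves out one kind of individual change that the entry criteria allow.

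**Working it through.** The documents give no figure to reproduce. The check sets each possible change in one participant, on one analyte, against the displays that the synopsis states.

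| Change | Normal-to-abnormal description | Before/after summaries | Optional paired test | AE tables |
|---|---|---|---|---|
| Normal to abnormal | Counted | Group level only | Group level only | Only if recorded as an AE |
| Abnormal, then further out in the same direction | Cannot be counted | Group level only | Group level only | Only if recorded as an AE |
| Abnormal, then abnormal in the opposite direction | Cannot be counted | Group level only | Group level only | Only if recorded as an AE |

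**Can the last two rows occur?** Yes. Inclusion criterion 9 admits the abnormal baseline. It limits such baselines to those judged not clinically significant, but does not remove them.

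**Do the group summaries show the change?** Only weakly. In a group of 10, a change of *d* in one participant moves the group mean by *d*/10. The group minimum or maximum may show the extreme value, but not the baseline it came from. A paired test uses within-participant differences but reports one result for the group, and it is run only if thought necessary.

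**Do the AE tables show it?** Only when the change is recorded as an AE. The synopsis gives no rule for when a laboratory change becomes one.

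**Would a listing of any worsening be informative?** Not without a threshold, because it would compare the worst of five post-dose values with a single baseline. Assumptions, none of them from the documents: no drug effect; normally distributed values; an upper limit only; a share *q* of participants above the limit at baseline; and a between-participant share of variance *r*. Write the value at visit *j* as X_j = √r·B + √(1−r)·E_j, with B and E_j independent standard normal and j = 0 the baseline. The quantity needed is P(max(X_1,…,X_5) > X_0 | X_0 > limit). Numerical integration gives:

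| *q* | *r* = 0.5 | *r* = 0.9 |
|---|---|---|
| 2.5% | 31% | 64% |
| 10% | 47% | 70% |

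Under these assumptions, roughly a third to two thirds of baseline-abnormal participants would be listed for a given analyte with no treatment effect at all. These figures bear on the design of the fix. They do not measure the size of the gap.

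**The case against.** The strongest objection is that this is a synopsis. Shift tables and participant listings are usually specified in the SAP, to which the synopsis defers, so nothing can be said to be missing from the plan as a whole. That stands, and the point is confined to the display as written. It remains worth making because the synopsis states a specific rule, and that rule excludes one kind of worsening.

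The second objection is that worsening already has reporting routes. CTCAE is adopted, AEs are tabulated by grade, every laboratory value enters the before/after summaries, and clinically significant baseline abnormalities are kept out. This also stands in part. What is left is worsening that is not recorded as an AE, from a baseline judged not clinically significant. None of the stated routes shows such a change for an individual.

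Two stronger readings are tempting. A reader might infer that laboratory data from participants with abnormal baselines go unanalysed. The documents do not support this, since those values are in the group summaries and possibly in the AE tables. A reader might also infer that laboratory safety is treated less carefully than efficacy, because change from baseline is named for UBT values and not for laboratory tests. That contrast carries no weight: with complete data the mean change equals the difference between the before and after means, and a summary of change would not identify individuals either.

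**Conclusion.** The point holds as a minor improvement to reporting. In the synopsis, the only categorical laboratory display cannot include a participant who worsens from an abnormal baseline, although inclusion criterion 9 allows such baselines. This follows from the text and needs no numerical assumption.

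The number of participants affected cannot be estimated, because the documents give no rate of abnormal baselines or of worsening from them. Sample size, tests, data collection and the validity of the trial are unaffected. The main uncertainty is whether the separate SAP already contains a fuller display.

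**What to change.** Keep the present normal-to-abnormal sentence for all analytes. Replacing it with a table of CTCAE grades alone would lose results that leave the normal range without reaching a grade. Add two displays:

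1. **A by-group shift table** of baseline against worst post-dose category over D4, D6, D8, D12 and D17, including participants abnormal at baseline. Use low/normal/high throughout, and CTCAE 5.0 grade where one exists. Define baseline as in note 1 of the Schedule of Activities: the D-1 result, or the screening result within 7 days used in its place.
2. **A by-participant listing** of baseline and all post-dose values for participants abnormal at baseline whose grade increases or who become abnormal in the opposite direction. For analytes without a grade, list those whose change exceeds a minimum set in advance.

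State beside both displays that taking the worst of five visits against a single baseline will show some worsening by chance. If the separate SAP already has these displays, bring the synopsis sentence into line with it.

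The cost is one table and one listing from data already collected, with grade programming for the graded analytes. Cells will be sparse at 10 per group. Worsening within a grade will not trigger the listing, which is the price of keeping noise out of it.

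### The only inferential PK method compares groups on different TNP-2198 doses; Day 1 Cmax, Cmin,ss and metabolite exposure have no clear dose-corrected comparison, and no slope or D/B ratio with an interval is named

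*Combined protocol and SAP*

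**What the plan says.** The second primary objective in the synopsis is: "To evaluate the pharmacokinetics of multiple doses of TNP-2198 (including major metabolites), rabeprazole, and amoxicillin in each treatment group". Under Study Design, 40 participants are randomised equally to four groups. A, B and C take TNP-2198 at 200, 400 and 600 mg twice daily with rabeprazole 20 mg. D takes the Group B regimen plus amoxicillin 1 g.

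The section on PK sampling states: "The test sample is plasma and the test substances are: TNP-2198 (including major metabolites), rabeprazole and amoxicillin". The PK Parameters section gives minimum lists:

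- First dose: Tmax, Cmax, half-life, two AUCs, Vd/F and CL/F.
- Last dose: the steady-state counterparts, a third AUC, Cmin,ss ("Minimum plasma concentration at steady state"), Cavg,ss, the accumulation index and the fluctuation index (DF).

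Under Pharmacokinetic parameter analysis, parameters are summarised by group, including the geometric mean and geometric CV. The one inferential sentence is "Analysis of variance or non-parametric test will be performed on pharmacokinetic parameters between each treatment group". It names no scale, dose normalisation, contrast, slope, ratio or interval. The Statistical Analysis section closes with "There are no clear statistical hypotheses in this study and all statistical tests are exploratory test with a two-sided 5% nominal significance level" and leaves the detail to a separate SAP.

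**The concern.** PK is a primary objective. The design gives two natural comparisons: three TNP-2198 dose levels (A to C), and one pair on the same dose with and without amoxicillin (B and D). A between-group test on uncorrected exposure uses neither well. If exposure simply follows dose, the groups differ and the test is significant. If exposure rises somewhat faster than dose, the test is again significant. The p-value does not tell the two apart, and no estimate with an interval is named beside it.

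What is at stake is how readable the PK results are, not a decision. Nothing in the documents depends on this p-value.

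**Working it through.** The plan gives no power, variability or effect size for PK, so there is no stated figure to reproduce.

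**Inputs from the synopsis:** 10 per group; TNP-2198 doses 200/400/600/400 mg; 12 h dosing interval; two-sided 5%.

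**Assumptions:** log-normal exposure with σ² = ln(1 + CV²); CV 30% to 100%; median exposure proportional to dose^b; no dropout. Rejection rates come from at least 20,000 simulated trials per setting.

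**1. What the test shows on uncorrected exposure.** Four-arm ANOVA, raw scale, exact proportionality (b = 1):

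| CV | 30% | 50% | 60% | 80% | 100% |
|---|---|---|---|---|---|
| Rejects | 100% | 97% | 87–88% | 60% | 39% |

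At b = 1.3 it rejects 100% (CV 30%) and 99.8% (CV 50%), so it does not separate 1.0 from 1.3. It is not empty: at b = 0 it rejects about 5%, and at b = 0.5 it rejects 91% (CV 30%) and 45% (CV 50%), so flat or strongly saturating exposure could show.

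**2. What the listed parameters already cover.** By the usual definitions (the synopsis gives no formula for these two), CL/F,ss = dose/AUC0-tau,ss and Cavg,ss = AUC0-tau,ss/12 h. A test on CL/F,ss is therefore a dose-corrected test of parent AUC0-tau,ss and Cavg,ss; under b = 1 it rejects about 5%.

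The synopsis defines DF = 100 × (Cmax,ss − Cmin,ss)/Cavg,ss, so (Cmax,ss − Cmin,ss)/dose = DF/(100 × 12 × CL/F,ss). DF together with CL/F,ss thus gives partial cover for Cmax,ss. To gauge it, further assume Cmax/Cavg = 3 and Cmin/Cavg = 0.2 at 400 mg, and correlation 0.7 among the three. Rejection at CV 30/40/50%:

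| True state | DF | CL/F | Dose-normalised parameter |
|---|---|---|---|
| AUC proportional; Cmax and Cmin slope 0.7 | 72/45/30% | about 5% | Cmax/dose: 50/31/22% |
| Only Cmin departs, slope 1.5 | about 5–6% | about 5% | Cmin/dose: 94/73/54% |

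Cmin,ss is therefore not covered. DF is not listed for Day 1, so Day 1 Cmax is not covered either. The synopsis does not say that CL/F will be computed for metabolites, so their cover is unclear.

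**3. Omnibus or pairwise.** The sentence can be read either way. For CL/F at CV 30% / 50%:

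| Test | b = 1.3, no amoxicillin effect | b = 1, D exposure 1.5 × B |
|---|---|---|
| Four-arm ANOVA on CL/F | 50% / 20% | 80% / 32% |
| A vs C, log CL/F | 66% / 31% | 5% / 5% |
| B vs D, log CL/F | 5% / 5% | 83% / 44% |
| Slope = 1 over A to C | 68% / 33% | 5% / 5% |

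The omnibus test mixes non-proportionality over A to C with an amoxicillin effect in D. Pairwise tests largely separate them. A vs C alone carries 10 × (ln 3)²/2 = 6.03 of the 6.17 slope information (step 4), or 98%.

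**4. Precision of the proposed estimates.** The deviations of ln(200, 400, 600) from their mean are −0.597, 0.096 and 0.501. Their squares sum to 0.617, so Sxx = 10 × 0.617 = 6.17.

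At CV 50%, σ = √ln 1.25 = 0.472:

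- Slope 90% CI half-width = t(0.95, 28) × σ/√Sxx = 1.701 × 0.472/2.485 = 0.32. Over the 3-fold dose range this is 3^0.323 = 1.43-fold.
- D/B 90% CI factor, error from B and D only (18 df) = exp(1.734 × 0.472 × √(2/10)) = 1.44. Pooled over four arms (36 df) it is 1.43.

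At CV 30% the same formulas give ±0.20 and a factor of 1.26 (18 df) or 1.25 (36 df).

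**The case against.** The case against has real weight.

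- **Cover exists.** One might infer that TNP-2198 exposure has no dose-corrected comparison at all. That goes too far: CL/F,ss and DF sit inside the same planned test. This stands and narrows the point to Day 1 Cmax, Cmin,ss and metabolite exposure.
- **Attribution.** One might also infer that a significant CL/F result can never be traced to dose or to amoxicillin. That holds only for a four-arm omnibus test, and the wording equally allows pairwise tests. B vs D needs no dose correction for any parameter.
- **No information is lost.** The planned geometric means and geometric CVs, with group sizes, determine the slope, the D/B ratio and both intervals, because dose is constant within each group. This stands: what is missing is a named analysis, not data.
- **No objective is unmet.** The objective asks for PK in each group, which the descriptive summaries answer. Neither proportionality nor an amoxicillin interaction is an objective, and every test is exploratory. This stands and sets the priority low.
- **The synopsis is not the whole plan.** The parameter lists are minimums, and detail is left to an SAP that was not supplied. The documents do not support saying that the SAP omits these analyses.

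What survives is that the one inferential sentence, applied to uncorrected exposure across different doses, gives a p-value that says little, and that better estimates cost almost nothing.

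**Conclusion.** The point holds as a low-priority improvement to the synopsis wording; it is neither a contradiction nor a numerical error. For uncorrected exposure the named test mostly registers the dose difference up to an assumed CV of about 60%, and less reliably above that on the raw scale. All rates rest on assumed CVs, and the slope of 1.3 and D/B ratio of 1.5 are chosen illustrations. The documents do not support reading this as a failure of the primary PK objective or as an error that would change a decision.

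**What to change.** Amend the PK analysis sentence as follows:

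- For TNP-2198 and metabolite Cmax and AUC0-tau on Days 1 and 15, replace the between-group test with a power model of ln(parameter) on ln(dose) over Groups A to C, reporting the slope with its 90% CI.
- For the same parameters, report the D/B geometric mean ratio with its 90% CI, and state the error term (B and D only, 18 df, or pooled over four arms, 36 df).
- Report Cmin,ss dose-normalised. Cavg,ss needs no separate test.
- Keep the between-group test for CL/F, V/F, half-life, accumulation index, DF, Tmax (rank test) and rabeprazole, which has the same dose in every arm. State whether it is omnibus or pairwise.
- Report amoxicillin descriptively, since only Group D receives it.

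If the separate SAP already specifies this, align the synopsis with it.

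The cost is a few sentences and routine code, with no new samples or participants. The downside is wide intervals. At CV 50% the slope test would still miss a true slope of 1.3 in about two-thirds of trials, so the results should be presented as estimates and not as proof of proportionality or of no interaction.
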